Overview of the study design. Prior to the waitlist-controlled trial, we will conduct a qualitative, user-centered design process with up to 10 pairs of older adults with symptoms of SCD/MCI and ELLs to iteratively refine the training protocols and the materials that will support productive, engaging conversations. We then will conduct a mixed-methods pilot randomized trial with a waitlist control group in which 44 pairs of older adults with symptoms of SCD/MCI and ELLs will be recruited from a variety of sources. Pairs will participate in webcam conversations supported by research staff for 8 weeks, using materials designed to promote positive and effective conversation sessions. Data will be collected from older adults with symptoms of SCD/MCI and ELLs via observations of videoconference sessions, qualitative semi-structured interviews, and quantitative surveys at baseline and the 8-week follow-up. The primary goal of the randomized pilot study will be to evaluate our capacity to recruit pairs, implement the intervention, and retain participants with symptoms of SCD/MCI in sufficient numbers for a subsequent trial evaluating the intervention's impact on participants' psychological well-being, mood, and cognitive functioning. We also will use mixed methods to evaluate the communication process between older adults with symptoms of SCD/MCI and ELLs including factors that contribute to satisfaction of both parties, engagement in sessions, contributors to dissatisfaction or dropout, and perceptions among older adults with symptoms of SCD/MCI of being appreciated and effective. Finally, using data from the waitlist-controlled trial, we will estimate variances for key outcome variables for planning the subsequent clinical trial, and we will conduct exploratory analyses of intervention-control differences in participants' perceptions of their wellbeing, mood, and cognitive functioning.

Sequence of the investigation. Months 1-6 will be devoted to developing protocols and materials for screening/surveys, recruitment, training, and supervision of sessions. In Months 7-11 we will conduct a user-centered design process (Aim 1) and refine protocols and materials in preparation for the trial. Months 12-17 will be devoted to enrolling 44 pairs of older adults with symptoms of SCD/MCI and their ELL partners for the pilot trial. Older adults' cognitive functioning,

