Alternative plans for recruiting older adults with symptoms of SCD/MCI. A primary goal of this R21 is to demonstrate our ability to recruit and maintain pairs of older adults with symptoms of SCD/MCI and ELLs, since recruitment is the single greatest challenge for studies such as this that includes "dyadic" participation and people with symptoms of SCD/MCI. In the event that accrual is slower than anticipated, we have identified several alternative sources of recruits. Drs. [name] and [name] are both investigators within the VA healthcare system and well-versed in identifying VA patients based on electronic medical record data and outreach to clinics. VA's national network of Geriatric Research Education and Clinical Centers (GRECCs) includes a center in Ann Arbor and would be a fruitful secondary source of participants with symptoms of SCD or diagnoses of MCI or who are identified as high risk by their providers. Additional participants could be identified via referrals from the University of Michigan (UM) Geriatrics Center and through the UM Health Research database, which includes more than 34,000 individuals expressing an interest in participating in

research. Other sources of older adults who could be screened for symptoms of SCD/MCI include Michigan's network of Area Agencies on Aging, Michigan chapters of the national Alzheimer's Disease Association (see letters of support), and community outreach to residential facilities and community-dwelling older adults.

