Aim 2-3 waitlist controlled trial. While our primary scientific goal is not to evaluate intervention-control differences in outcomes, we will include a waitlist control group in order to get an unbiased estimate of recruitment rates for that subsequent randomized clinical trial. We will generate a randomization sequence and randomization envelopes to assign 44 older adults to the intervention or waitlist control group (1:1 ratio). Randomization will be conducted after older adults with symptoms of SCD/MCI complete their baseline survey. Older adults with symptoms of SCD/MCI assigned to the intervention will be matched with an ELL for 8 weeks of hourly SPEAK! sessions with orientation and materials refined as part of Aim 1. Older adults with symptoms of SCD/MCI assigned to the waitlist control will be matched with an ELL after completing their 8-week follow-up survey, at which time the pair will complete the 8-week intervention.

Quantitative measures for Aims 2-3. Older adult with symptoms of SCD/MCI surveys. Sociodemographic characteristics of older adults with symptoms of SCD/MCI will be measured using standard items to evaluate the generalizability of the study findings and possible moderators of intervention effects. General health status will be measured at baseline using standardized items to identify common chronic diseases. At baseline and follow-up, older adults with symptoms of SCD/MCI will complete the Psychological Well-Being Scale (PWB), a validated measure shown to be sensitive to intervention effects and with subscales measuring respondents’ sense of autonomy, environmental mastery, personal growth, positive relations with others, life purpose, and self-acceptance. The PWB will be supplemented with measures

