Primary outcome and sample size for the pilot trial. The pilot trial (Aims 2-3) has been designed to be consistent with the goals of pilot studies articulated by Thabane et al., i.e.: to assess key processes (rates of recruitment, retention, and engagement); determine resources needed for a definitive trial (e.g., staff time required for recruitment and intervention delivery), and possible issues related to patient safety, dose-response, and variation of treatment effects. We expect that the outcomes for a larger, statistically-powered trial will be the Psychological Well-Being Scale (PWB) with secondary outcomes being measures of cognitive functioning and mood. The current trial is not intended to estimate those effect sizes, but rather to optimize the intervention and ensure that we have the capacity to reach the subsequent trial’s recruitment goals given expected timeline and resources. For that larger trial, we estimate we would need resources to recruit, retain, and implement the intervention with approximately 262 pairs recruited over 36 months. A target sample of this size would be sufficient to detect a small/medium impact on Psychological Wellbeing scores (PWB; Cohen’s $d=0.45$) with 0.90 power, a 0.05 probability level, and assuming a 20% dropout rate. To assure that we have the capacity to enroll at that same rate, we will recruit 44 pairs in the waitlist trial for Aims 2-3 over 6 months. According to the Poisson distribution, if our observed recruitment over 6 months falls below 35 pairs, that would indicate that we would be unlikely to be able to recruit our target sample of 262 in the subsequent trial over 36 months ($P<.10$). We will conduct monthly reviews of our observed versus expected recruitment rate, and should recruitment fall more than 10% below expectation in the first two months, we will seek out additional sources of older adults with symptoms of SCD/MCI as described above.

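### Does the recruitment rule claim to prove capacity for 262 pairs when it can only warn of a shortfall?

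*Combined protocol and SAP*

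**What the plan says.** The relevant text is in Section III, under the paragraph on the primary outcome and sample size for the pilot trial. The later trial is put at about 262 pairs over 36 months, from d=0.45, power 0.90, a 0.05 level and 20% dropout. The pilot is meant to "ensure that we have the capacity to reach the subsequent" trial's recruitment goals, and the plan adds: "To assure that we have the capacity to enroll at that same rate, we will recruit 44 pairs in the waitlist trial", over six months.

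The count is then read in one direction only: "if our observed recruitment over 6 months falls below 35 pairs, that would indicate that we would be unlikely to be able to recruit" the 262 over 36 months, with P<.10. There are also monthly reviews of observed against expected accrual, and "should recruitment fall more than 10% below expectation in the first two months, we will seek out additional sources".

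Elsewhere the aim is put more neutrally. The overview of the study design (Section II) says: "The primary goal of the randomized pilot study will be to evaluate our capacity to recruit pairs, implement the intervention, and retain participants". The waitlist-trial paragraph of Section III gives the control group's purpose as "in order to get an unbiased estimate of recruitment rates for that subsequent randomized clinical trial", and fixes the number to be randomised: "to assign 44 older adults to the intervention or waitlist control group (1:1 ratio").

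**The concern.** Capacity to recruit is part of the pilot's primary goal, so the reading of the six-month count matters. The plan limits the chance of wrongly doubting an adequate rate. It gives no figure for the opposite error, in which an inadequate rate passes without a warning. No meaning is written down for 35 to 43 pairs, a range that occurs 42% of the time at exactly the needed rate and 52% of the time at 40. No interval is planned for the rate or for the projected 36-month total. Because randomisation stops at 44, the count alone cannot show a rate above the one needed.

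If the absence of a warning were taken as assurance, the next trial's timeline, sites and sources could rest on too hopeful a projection. Nothing inside this pilot (participants, allocation, outcome analyses) would be touched.

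**Working it through.** **Inputs from the sample-size paragraph.** 262 pairs in 36 months; 44 pairs in six months; warning below 35; Poisson; P<.10; d=0.45, power 0.90, level 0.05, dropout 20%. Two-sided testing and 1:1 allocation in the later trial are assumed. The true rates of 30 to 40 used below are illustrative and do not come from the documents.

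**1. The plan's own figures.**
- Later trial, normal approximation: 2(1.960+1.282)²/0.45² gives 104 per arm, 208 in all; 208/0.8 = 260. The t-based calculation gives 105 per arm, 210 in all; 210/0.8 = 262.5. The stated 262 is reproduced.
- Needed rate: 262/36 × 6 = 43.67 per six months, rounded up to 44.
- Warning: P(X ≤ 34 | 43.67) = 0.079. The next cut gives P(X ≤ 35 | 43.67) = 0.105. So below 35 is the largest cut with P<.10.

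**2. The warning as a prediction.** After x pairs in one six-month unit, give the rate a gamma distribution with shape x+c and unit rate, c from 0 to 1. The count over the next six units is then negative binomial with size x+c and probability 1/7. After 34 pairs, P(at least 262) is 0.07 to 0.10. The plan's statement that 262 would then be unlikely holds on this view too.

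**3. What escaping the warning shows.** Escape is P(X ≥ 35 | rate). The chance of success is P(Poisson(6 × rate) ≥ 262).

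| True rate per 6 months | Escapes warning | P(≥262 in 36 months) | Months to 262 |
|---|---|---|---|
| 30 | 20% | <0.0001 | 52.4 |
| 35 | 52% | 0.0003 | 44.9 |
| 38 | 71% | 0.015 | 41.4 |
| 40 | 81% | 0.084 | 39.3 |

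The large escape figures belong to rates close to target. A rate well short of it, such as 30, is flagged about 80% of the time.

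**4. Adding the two-month check.** Expected accrual in two months is 44/3 = 14.67, and 90% of that is 13.2, so the trigger is read as 13 or fewer. It fires 54% of the time at a rate of 40, 72% at 35 and 41% at the needed 43.67. With the rate held constant, both checks are escaped 44% of the time at 40 and 23% at 35.

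**5. Size of a near miss.** A rate of 40 gives 40 × 6 = 240 pairs in 36 months. Reaching 262 takes 262/(40/6) = 39.3 months, about 3.3 more than planned. Stopping at 240 leaves 240 × 0.8 = 192 with outcomes, 96 per arm, for which two-sided t-test power at d=0.45 is about 0.87 against 0.90.

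**6. Precision at the target.** Exactly 44 pairs at month 6 has an exact Poisson 95% interval of 32.0 to 59.1 per six months, and a predictive chance of at least 262 of 0.50 to 0.56.

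**The case for a change.** The strongest case for a change is that the paragraph names a purpose and then gives no result that would meet it. Hitting 44 on schedule leaves the chance of 262 in 36 months near one half, and a rate of 38, with a 1.5% chance of success, escapes the warning 71% of the time. A team reporting 38 or 40 pairs could say that no warning fired and call capacity assured. The monthly reviews and two-month trigger do not answer this: they prompt action rather than interpret the final count, and the trigger fires about 41% of the time when accrual is on target. Sources added mid-pilot would also make the final count harder to project. The Section II paragraph on alternative recruitment plans leans the same way, since it speaks of demonstrating the ability to recruit. A few sentences would put it right.

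Much of this stands. Escaping the warning is weak evidence of capacity, *assure* and *ensure* are stronger than six months of data can support, and an interval would be useful. What does not stand is that the plan commits the error. The sentence with *assure* states why 44 was chosen; it is not a decision rule. The 81% is the miss rate of a success reading that the plan does not make, at a rate only about 8% below target. The same paragraph opens by listing recruitment rates among the processes to be assessed, and the Specific Aims speak of determining whether recruitment is sufficient. Slow accrual also has a planned response: "In the event that accrual is slower than anticipated, we have identified several alternative sources of recruits".

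**Conclusion.** No change is needed. Every figure stated for recruitment (262, 44, below 35, P<.10) is correct, and the below-35 rule does what is claimed for it: it signals infeasibility. The gap is a missing gloss on 35 to 43 pairs and a missing interval. Recruitment rates are to be tracked overall and by subgroup, so an analyst can attach an exact Poisson interval and a projected total without any amendment, using the time taken if 44 is reached early. The statement in the additional-analysis paragraph that results will exclude inference names p-values and follows the descriptive enrolment and dropout analyses, so it is no clear bar to an interval.

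The reader should simply not take the absence of a warning as proof of capacity: escape runs from 20% at a rate of 30 to 81% at 40, or 23% at 35 and 44% at 40 when the two-month check is counted. The cost of a near miss falls on the next trial and is mainly time, about three months at a rate of 40.

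These figures assume a constant Poisson rate and similar resources in the later trial. Added sources, overdispersion, or the multi-site successor foreseen in the Dissemination Plan would alter them. They would not turn the plan's warning into a claim of proof.

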The proposed study is designed to tailor SPEAK! to the unique needs of people with symptoms of SCD/MCI and gather preliminary data on its feasibility and impact in that population. Despite our extremely encouraging experience to date recruiting older adults for SPEAK! (many of whom have contacted us with little or no prior outreach), an important goal of the R21 will be to determine whether we are able to recruit and retain older adults with symptoms of SCD/MCI as well as their ELL conversation partners at a rate sufficient to ensure accrual goals for the subsequent R01-funded randomized trial. We also will tailor current SPEAK! orientation and session-support materials to address the unique consent and informational needs of people with symptoms of SCD/MCI, and we will gather preliminary data on satisfaction with the SPEAK! experience and its impact on participants' mental health and functioning. The study will provide vital data for the submission of a competitive application for a larger randomized trial evaluating the intervention's impact on SCD/MCI patients' mental health (e.g., depression, loneliness, and sense of purpose) and cognitive functioning. Consistent with the NIA Stage Model for Behavioral Intervention Development, the current study will include elements of Stage 0 (intervention generation, refinement, modification, and pilot testing) and Stages 1-2 (efficacy testing with various levels of control). Specifically, the study will include a mixed-methods user-centered design

process (Aim 1, NIA Stage 0) followed by a randomized waitlist-controlled trial with an 8-week follow-up (Aims 2 and 3, NIA Stages 1-2). The study's specific aims are:

Aim 1: Conduct a user-centered design process to refine the SPEAK! training protocols for older adults with symptoms of SCD/MCI and ELLs, and the materials that will support productive, engaging English conversation practice.

Aim 2: Conduct a randomized, wait-list controlled trial of 8 weeks of SPEAK! participation, using a variety of recruitment sources, in order to evaluate our capacity to recruit, implement the intervention, and retain older adults with symptoms of SCD/MCI in sufficient numbers for a subsequent randomized-controlled trial evaluating the intervention's impact on participants' psychological well-being, mood, and cognitive functioning.

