sense of well-being, and other key variables will be measured using validated scales at baseline and the 8-week follow-up. Data collection will be completed in month 20, waitlist control participants will complete the intervention in month 23, and months 23-24 will be devoted to statistical analysis, presentations, and the submission of an application for a larger, definitive randomized trial focusing on measures of cognitive functioning, well-being, depressive symptoms, and physical health outcomes.

Eligibility and screening of older adults with symptoms of SCD/MCI. To be eligible, older adults with symptoms of SCD/MCI must: be 55+ years of age, fluent speakers of English of any race/ethnicity, and be able to participate in a videoconference via a smartphone, tablet, laptop, or desktop computer in their home or referring organization using a widely-accessible, no cost videoconferencing platform. Participants will be ineligible if they have a history of stroke or traumatic brain injury, bipolar disorder, schizophrenia, or current alcohol or drug abuse/dependence, that would affect their ability to participate in the study. Our primary source of recruits will be the Michigan Alzheimer's Disease Core Center (MADCC) registries which include detailed information about individuals who have indicated a willingness to be contacted regarding studies and have undergone detailed neuropsychologic evaluations. [name] (Co-I) is the Clinical Core Leader for the MADCC and [name] (Co-I) is the MADCC Director for Outreach and Recruitment. More than 100 MADCC registry participants have been identified with MCI and this number is expected to increase. Additional participants will be identified via outreach and referrals from specialty clinics including the UM Cognitive Disorders Clinic, two area community senior centers, as well as Michigan Chapters of the national Alzheimer's Association (see letters of support).

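### Does the warning at fewer than 35 pairs in six months lose its stated error rate because waitlisted older adults meet their ELL partner eight weeks late?

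*Combined protocol and SAP*

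**What the plan says.** The pilot's main question is recruitment capacity. *Specific Aims* (section I) includes the learners in that question: the aim is to recruit older adults "as well as their ELL conversation partners at a rate sufficient to ensure accrual goals" of the later trial.

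*Primary outcome and sample size for the pilot trial* (section III) puts the later trial at "approximately 262 pairs recruited over 36 months". It continues: "To assure that we have the capacity to enroll at that same rate, we will recruit 44 pairs" over 6 months. The warning follows: "if our observed recruitment over 6 months falls below 35 pairs, that would indicate that we would be unlikely to be able to recruit" the later target, at P<.10. Observed and expected recruitment are compared monthly. A shortfall of more than 10% in the first two months sends the team to further sources of older adults.

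*Aim 2-3 waitlist controlled trial* (section III) randomizes 44 older adults 1:1 after their baseline survey. It gives the reason for the waitlist arm as "in order to get an unbiased estimate of recruitment rates for that subsequent randomized clinical trial". On the second arm it says that those "assigned to the waitlist control will be matched with an ELL after completing their 8-week follow-up survey, at which time the pair will complete". What is then completed is the same programme of sessions.

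*Sequence of the investigation* (section II) sets the calendar: "Months 12-17 will be devoted to enrolling 44 pairs of older adults with symptoms of SCD/MCI and their ELL partners". It then says: "Data collection will be completed in month 20, waitlist control participants will complete the intervention in month 23".

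**The concern.** The warning is expressed in pairs, but the unit randomized is the older adult, and half of the older adults are not matched until eight weeks after entry. Anyone on the waitlist who enters in the last eight weeks of the window cannot be in a matched pair when it closes. No sentence says whether such a person counts as a recruited pair, or whether their ELL is enrolled early and held.

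This is the only numerical criterion for the end of the pilot. If the count were of matched pairs at month 17, a team recruiting exactly on target would see the warning about one time in three instead of one in thirteen. If instead the older adult's entry alone counted as a pair, the criterion would not test whether learners can be found for the waitlist half, although learner recruitment is part of the stated aim.

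A second worry is that 35 or more is weak evidence of capacity, and that the plan names no interval for the recruitment rate.

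**Working it through.** **Inputs.** The later trial needs 262 pairs in 36 months. The pilot seeks 44 pairs in 6 months and warns below 35, that is, at 34 or fewer (all from *Primary outcome and sample size*). Allocation is 1:1 and waitlist matching comes 8 weeks after entry (*Aim 2-3 waitlist controlled trial*). Enrolment runs from month 12 to month 17 (*Sequence of the investigation*).

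**1. The plan's own figure.** The required rate is 262/36 = 7.278 pairs per month, so the six-month mean is 6 × 7.278 = 43.67. The lower Poisson tail is P(X ≤ 34) = 0.079. One step higher, P(X ≤ 35) = 0.105, so 35 is the largest cut-off that keeps the probability below .10 at this mean. With a mean of 44, P(X ≤ 34) = 0.072. The stated P<.10 is reproduced.

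**2. Matched pairs only, closed at month 17.** Assume even accrual, immediate matching in the intervention arm, a learner ready as soon as the 8-week survey is done, and no waitlist loss.

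- Eight weeks is 8/(52/12) = 1.846 months.
- The share of waitlist entrants still unmatched at six months is 1.846/6 = 30.8%, or 22 × 0.308 = 6.8 people.
- The expected number of matched pairs is 43.67 × (0.5 + 0.5 × 0.692) = 36.95.
- P(X ≤ 34) = 0.352. Taking 8 weeks as 2 months gives a mean of 36.39 and P = 0.387.

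**3. Matched pairs, not closed at month 17.** Suppose the count covers pairs formed from everyone enrolled in the six months, read once the last waitlist participant has been matched. With no loss the mean returns to 43.67 and the probability to 0.079. Late matching alone therefore does not disturb the error rate; it takes late matching together with an early close. If 20% of waitlisted people left before matching (an assumption, borrowing the dropout figure that the plan uses for the later trial), the mean would be 43.67 × (0.5 + 0.5 × 0.8) = 39.3 and the probability 0.225.

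**4. Which reading the plan supports.**

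- The sample size paragraph uses enrolling and recruiting as the same act. Matching appears under the waitlist design as a separate, later step.
- The calendar places all 44 pairs, learners included, inside months 12 to 17, yet has the waitlist arm finishing in month 23. The planners thus allowed for waitlist sessions running past the enrolment window and still called the pairs enrolled.
- Under a matched count closed at month 17, enrolling exactly 44 older adults evenly would yield 22 + 22 × 0.692 = 37.2 pairs. The plan's own target would be out of reach for a team on schedule.
- The two-month review would also misfire. Expected recruitment is 2 × 7.278 = 14.6. Matched pairs would number 7.28 + 3.639 × (2 − 1.846) = 7.8, which is 46% short against a 10% trigger.

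**5. Strength of the screen.** Counting at enrolment, 35 or more occurs with probability 0.775, 0.518 and 0.234 when the true rate is 90%, 80% and 70% of target (illustrative scenarios). An exact 95% interval for 36-month accrual, assuming the pilot rate continued, is 146 to 292 after 35 pairs and 192 to 354 after 44.

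**The case for a change.** The strongest case for a change is that a timetable is not a counting rule. The plan's only end-of-pilot number should not depend on inference from a schedule, and a rule left open could be settled after the count is known. If the older adult's entry is what counts, up to half of the counted pairs may have no learner yet. The plan itself, under *Alternative plans for recruiting older adults with symptoms of SCD/MCI* (section II), names dyadic recruitment as part of the main difficulty. Defining the event would cost a sentence or two.

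Part of this stands. No passage gives the enrolment date of a waitlist participant's learner, and a count of older adults alone would say nothing about learners for that arm. The rest is weaker. A convenient choice after the fact is hard to square with monthly comparisons of observed and expected recruitment, which need a running count from the start. The 35% figure describes a reading that makes the plan's own target and its two-month check unworkable.

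The case about 35 or more also corrects nothing. The plan makes a one-directional statement: below 35 is a warning. It does not claim that 35 or more proves capacity, and it attaches no stop or go decision to either side. A two-sided 95% interval would already include 262 at 31 pairs (126 to 264), so alongside a one-sided 10% warning it would need a further rule to say which prevails. Reporting an interval is a reasonable option, not a repair.

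**Conclusion.** No change follows. The warning is correctly calculated: the on-target chance of falling below 35 is 0.079, within the stated .10, on the enrolment reading that the schedule, the target of 44 and the monthly review all support. The rise to 0.35–0.39 needs two departures from that reading at once, a matched-pair count and a close at month 17, and rests on even accrual and prompt matching.

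The remaining gap is the enrolment date of learners for the waitlist arm. It is the kind that analysts fill sensibly. The plan already calls for a learner baseline survey, and for tracking databases and a flow chart covering all participants, so learner enrolment can be reported next to that of the older adults without touching the cut-off. The conclusion assumes that the team follows its own calendar and counts at enrolment. If it reported only matched pairs at month 17, the cut-off of 35 would no longer carry its stated probability, but nothing in the plan directs that.

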Additional analysis for Aims 2-3. Older adults with symptoms of SCD/MCI will be asked to consent to a brief screening survey, and initial analyses will focus on the sociodemographic, health, and mental health characteristics of potential participants who do versus do not enroll, and reasons for non-participation. Recruitment rates will be tracked overall as well as by gender, age, race/ethnicity, and educational attainment. Among enrollees, we will calculate descriptive statistics of the proportion of older adults with symptoms of SCD/MCI who choose to discontinue participation, as well as baseline predictors of dropout and session completion, with a particular emphasis on baseline measures of cognitive functioning, and psychological indicators such as PWB and depressive symptoms. While these will be quantitative analyses, results will not include statistical inference (i.e., “p-values”). **For Aim 3.** We will examine correlations between measures of (a) intervention satisfaction and the number of missed sessions, and (b) baseline measures of characteristics of older adults with symptoms of SCD/MCI including measures of cognitive functioning and PWB. Examination of intervention/control differences in PWB will be purely exploratory and used to generate hypotheses and strategies for modifying the intervention to make it more impactful. Change scores for continuous outcomes (e.g., PWB) will be computed, and differences across randomization groups will be compared using the Wilcoxon rank sum test.

In a purely exploratory mode, we will examine differences in outcomes between intervention and control groups, controlling for any baseline differences in group characteristics. Older adults who drop out of the program or who complete less than the expected number of sessions but complete outcome surveys will be included in outcome analyses. We also will conduct 'completer' analyses including only intervention-group older adults who complete 8 out of the 12 planned sessions (or the equivalent out of 8 planned sessions). Whenever possible, we will create graphical displays comparing pre-post changes in outcomes across groups to make the findings as interpretable as possible for various audiences.

IV. Potential Risks, Minimizing Risks, and Potential Benefits

Protection of Human Subjects

Human Subjects Involvement and Characteristics

1. Risk to Subjects

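### The recruitment rule projects one pooled 6-month count to 36 months at a constant rate, and the specified tabulations omit recruitment source, so a count of 35 or more could overstate sustainable capacity unnoticed

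*Combined protocol and SAP*

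**What the plan says.** Under *Primary outcome and sample size for the pilot trial* (Section III), the later trial is put at "approximately 262 pairs recruited over 36 months". The pilot is sized to match: "To assure that we have the capacity to enroll at that same rate, we will recruit 44 pairs in the waitlist trial", over 6 months. The decision rule follows: "According to the Poisson distribution, if our observed recruitment over 6 months falls below 35 pairs", the team would be "unlikely to be able to recruit our target sample of 262 in the subsequent trial over 36 months", with P<.10. The same paragraph provides monthly reviews and says further sources will be sought if accrual is more than 10% below expectation in the first two months.

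Under *Eligibility and screening of older adults with symptoms of SCD/MCI* (Section II), the primary source is the Michigan Alzheimer's Disease Core Center (MADCC) registries, made up of evaluated people who have agreed to be approached. On size: "More than 100 MADCC registry participants have been identified with MCI and this number is expected to increase". Specialty clinics, two senior centers and Alzheimer's Association chapters are named as additional sources. *Alternative plans for recruiting older adults with symptoms of SCD/MCI* lists others, including a university research database of more than 34,000 people.

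Under *Additional analysis for Aims 2-3* (Section III), the reporting breakdown is: "Recruitment rates will be tracked overall as well as by gender, age, race/ethnicity, and educational attainment". Recruitment source is not among the strata, although Aim 2 sets out to evaluate capacity across a variety of sources.

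**The concern.** A registry of already identified people is a stock as well as a flow. In the first months a study can draw on everyone accumulated so far; after that it depends on new entrants and on people not yet approached. Clinic referrals and community outreach are closer to a flow. A count pooled over both kinds of source says how many enrolled in 6 months, but not how much of that pace can be kept up for 36. If sources are added after month 2, the pooled count also covers two different sets of sources.

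This bears on the pilot's primary goal, which is capacity to recruit, deliver and retain for the later trial. The 35-pair rule is the only quantitative recruitment criterion given. If a satisfactory count came largely from the accumulated registry pool, the later trial could be planned on a rate that does not last, and tables by gender, age, race/ethnicity and education would not reveal it.

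**Working it through.** **1. The plan's own figures reproduce.** Inputs from *Primary outcome and sample size for the pilot trial*: d = 0.45, power 0.90, probability level 0.05, dropout 20%. I take the test as two-sided with 1:1 allocation; sidedness is not stated.

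- Two-sample t-test: 104.75 per arm, 209.5 in total, and 209.5 / 0.8 = 261.9, that is 262. The normal approximation gives 104 per arm and 208 / 0.8 = 260. A one-sided test gives 213, which does not match.
- Expected 6-month count at the later trial's rate: 262 × 6/36 = 43.67.
- Poisson: P(X ≤ 34 | 43.67) = 0.079. With mean 44 it is 0.072. Both are below .10.

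The arithmetic is sound. It rests on the rate being constant, since 43.67 × 6 = 262.

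**2. What a count of 35 or more shows even without depletion.** Exactly 35 projects to 35 × 6 = 210 pairs. A true mean of 35 per 6 months meets the cut-off with probability 0.52. A true mean of 30 (180 pairs over 36 months) meets it with probability 0.20.

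**3. Effect of a registry that can run down.** Let C be the pilot count, s the registry share of it, and K the total number the registry can ever yield: yield × (current pool + entrants during the later trial). Assume other sources keep their pilot rate and pilot participants are not enrolled again. The later trial's 36-month total is

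T = 6(1 − s)C + min{6sC, max(0, K − sC)}.

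The documents give no value for s, the yield or registry growth, so all of these are assumptions. With C = 44:

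| Registry share | Other sources, 36 months | Registry used in pilot | Pool 100, yield 50% | Pool 150, yield 50% | Pool 100, yield 100% | Pool 100 plus 20 per 6 months, yield 100% |
|---|---|---|---|---|---|---|
| 25% | 198 | 11 | 237 | 262 | 264 | 264 |
| 50% | 132 | 22 | 160 | 185 | 210 | 264 |
| 75% | 66 | 33 | 83 | 108 | 133 | 253 |
| 100% | 0 | 44 | 6 | 31 | 56 | 176 |

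Two cells in full:

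- 50% share, pool 100, yield 50%: 22 × 6 = 132 from other sources, plus 100 × 0.5 − 22 = 28 left in the registry, total 160.
- 25% share, pool 150, yield 50%: 33 × 6 = 198, plus 150 × 0.5 − 11 = 64, total 262.

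**4. Break-even share.** When the registry is the limit, T = 264 + K − 308s. Setting T ≥ 262 gives s ≤ (K + 2)/308.

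- K = 100: 102/308 = 33%.
- K = 75: 77/308 = 25%.
- K = 50: 52/308 = 17%.

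**5. What a shortfall would mean.** At 160 enrolled, 160 × 0.8 = 128 are evaluable. Two-sided t-test power at d = 0.45 is then 0.71 rather than 0.90. This is one scenario, not an estimate.

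**The case against.** The case on the other side has real force.

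- **Size of the pool.** A reader might infer that the registry is a closed pool of about 100 which the pilot will use up. The text does not support that. It says more than 100, counts only those identified with MCI, and expects growth. People with SCD are also eligible and are not counted. Nothing says registry members are approached first. This stands, and the eligible pool must be treated as unknown.
- **Other sources and sites.** Several other sources are planned, a large database is in reserve, and the *Dissemination Plan* describes the next trial as multi-site. A local registry need not limit that trial, and a single-site pilot could even understate its capacity. This stands as mitigation. It does not remove the point, because the next trial will need to know which sources delivered.
- **Tracking.** A reader might also infer that source will not be recorded. That goes too far. *Data and Safety Monitoring* provides weekly logs and a flow chart, and no sentence excludes recording source. What can be said is that source is missing from the listed strata and is not mentioned for the logs.
- **The rule.** The plan states only what a count below 35 means. It does not say that 35 or more proves capacity. That is correct, but the pilot count is offered as assurance that the later rate can be met, so the favourable reading is a natural one.
- **Re-enrolment.** That pilot participants would not enter the later trial is a reasonable assumption, not a statement in the plan.

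**Conclusion.** The point holds as a gap in reporting and interpretation. The rule relies on a constant rate, the primary source is one for which that may fail, and the specified tabulations do not let a reader check.

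The size cannot be fixed from the documents. With 44 enrolled it runs from a severe shortfall (160 of 262 at a 50% registry share, pool 100 and 50% yield; lower at higher shares) to none (262 or more at a 25% share with pool 150 and 50% yield, or with enough registry growth). These totals assume that other sources hold their pilot rate and that pilot participants are not re-enrolled.

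A reader should not conclude that 262 is out of reach, or that the Poisson calculation is wrong. The documents support neither. The change is still worth making, because it is cheap and bears directly on the pilot's primary conclusion.

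**What to change.** - Add recruitment source to the strata under *Additional analysis for Aims 2-3*, and record it for every contact, screen and enrolment.
- Report screening and enrolment by source and by month, marking any source added during the pilot.
- Beside the Poisson rule, show a 36-month projection summed over sources. Limit the registry's contribution to its remaining eligible pool plus documented new entrants, multiplied by the observed yield. State the pool size, including people with SCD, and its growth.
- State that 35 or more enrolled does not by itself establish capacity for 262.

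The cost is one field in the recruitment log and one table, with no change to sample size, eligibility or procedures. The field should be in place from the start: the link to identifiers is to be destroyed once data collection and cleaning are finished, so source may be hard to reconstruct later. The downsides are that source-specific rates will be imprecise with 44 people, so the projection needs ranges, and that it may look less favourable than the pooled figure.
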